5.1.2 Treatment Period

5.1.2.1 Day 0, Surgery (Intra-operative)

The following evaluations will be performed in the OR, during surgery:

- Collection of CPB data, including the following:
 - Equipment type
 - Cardioplegia solution type
 - Composition of isovolumetric exchange fluid for ultrafiltration and/or modified ultrafiltration
 - Exchange volumes in and out
 - Documentation of L-citrulline or placebo administration
 - CPB start and end times and decannulation time
- Hemodynamic monitoring, including the following:
 - Heart rate
 - Systemic blood pressure (BP)
 - O₂ saturation
 - Central Venous Pressure (CVP) measurements
 - Pulmonary Artery Pressure (PAP) measurements (if PA line is placed)

Baseline values are first recorded in the OR by Anesthesia. Results will be monitored during surgery according to the Institution's standard of care, but results will only be recorded approximately every 15 minutes.

- Arterial Blood Gases (ABGs)
 - PaO₂, PaCO₂, HCO₃, and pH measurements
 - Baseline values are first recorded in the OR by Anesthesia. All results obtained after induction of anesthesia and during surgery will be recorded.
- Bolus of L-citrulline at 150 mg/kg or placebo at initiation of CPB; addition of L-citrulline at a concentration of 200 µmol/L or placebo given as a bolus during bypass.
 This may be administered as a one-time bolus or multiple administrations to compensate for fluids containing L-citrulline that may be removed from the patient

during the course of the operation and thus to maintain the concentration of 200 µmol/L. The total dose will be dependent upon the total amount of any volume administered and removed during CPB.

- Blood draw (10 minutes after study drug is administered):
 - serum electrolytes, BUN, and creatinine
 - CBC with differential
 - ACT
 - plasma L-citrulline (1.0 mL)
- Inotrope and other concomitant medication documentation
- Adverse events documentation

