6.2 Efficacy and Safety Measurements Assessed

6.2.1 Efficacy Assessments

6.2.1.1 Mechanical Ventilation

The definition of mechanical ventilation includes invasive mechanical ventilation or non-invasive mechanical ventilation including BPAP or CPAP. Length of time on mechanical

ventilation will be assessed from the time of separation from CPB until mechanical ventilation is discontinued.

6.2.1.2 *Inotropes*

Inotropes are defined as dopamine, dobutamine, milrinone, epinephrine, phenylephrine, and norepinephrine. Inotrope use will be assessed from the start of CPB until the subject is discharged from the hospital or at Day 28.

Total Inotrope Score = Dopamine + Dobutamine + 10*Milrinone + 100*Epinephrine + 100*Phenylephrine + 100*Norepinephrine.

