7.1.4 Efficacy Variables

Analysis of Primary Efficacy Endpoint

The primary efficacy endpoint is a composite variable consisting of the longer of either (1) length of time on mechanical ventilation or (2) length of time of inotrope use.

The definition of mechanical ventilation includes invasive mechanical ventilation or non-invasive mechanical ventilation including BPAP or CPAP. Length of time on mechanical ventilation will be measured until the subject is discharged from the hospital or at Day 28. The length will be derived as the time in hours from separation from CPB until discontinuation of all mechanical ventilation including non-invasive support. If invasive or non-invasive mechanical ventilation is stopped but has to be restarted, time will continue to accrue. If a subject did not receive any mechanical ventilation the length is set to 0. For subjects who died before discharge from the hospital or before Day 28, respectively, the observed length of time on mechanical ventilation will be used. As sensitivity analyses subjects who died will (1) be excluded from analysis and (2) be assigned a length of time on mechanical ventilation of 28 days.

Asklepion GROWTH HEALTH PINNOVATION

11 August 2017

The definition of inotrope use includes medications which are considered within the derivation of the total inotrope score (dopamine, dobutamine, milrinone, epinephrine, phenylephrine, norepinephrine). Length of inotrope use will be measured until the subject is discharged from the hospital or until Day 28, whichever occurs first. The length will be derived as the time of first use until last use (in hours). Any duration of re-use will continue to accrue. If a subject did not use any inotropes the length is set to 0. For subjects who died before discharge from the hospital or before Day 28, respectively, the observed length on inotropes will be used. As sensitivity analyses subjects who died will (1) be excluded from analysis and (2) be assigned a length of time on inotropes of 28 days.

Hypothesis to be tested:

H0: Composite endpoint within the L-citrulline group is equal to that of the placebo group

H1: Composite endpoint within the L-citrulline group is unequal to that of the placebo group

H0 will be tested using a Wilcoxon-rank-sum test.

The level of significance is 1% (two-sided).

The FAS will be the primary analysis set for the analysis on the composite endpoint. Analyses using the mFAS and the PP serve as sensitivity analyses.

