4.4 Efficacy Analysis

4.4.1 Analysis of Primary Efficacy Variable

The primary efficacy endpoint is a composite variable consisting of the longer of either (1) length of time on mechanical ventilation or (2) length of time of inotrope use.

The definition of mechanical ventilation shall include invasive mechanical ventilation or non-invasive mechanical ventilation including BPAP or CPAP. The definition of inotrope use includes medications which are considered within the derivation of the total inotrope score (dopamine, dobutamine, milrinone, epinephrine, phenylephrine, norepinephrine).

The length of time on mechanical ventilation will be measured until the subject is discharged from the hospital or at Day 28. The length will be derived as the time in minutes from separation from CPB (variable "End time" of parameter "CPB" from section "Post incision" on CRF "Surgery") until discontinuation of all mechanical ventilation including non-invasive support (variables "Stop Time/Date of last use of non-invasive ventilation" and "Stop Time/Date of last use of invasive ventilation" of parameter "CPB" from section "Post incision" on CRF "Mechanical ventilation"). If invasive or non-invasive mechanical ventilation is stopped but has to be restarted, time will continue to accrue by subtracting the total duration of all ventilation breaks (variables "Stop date/time" and "Restart date/time" from CRF "Ventilation breaks").

- Length of time on mechanical ventilation (min) =
(Time mechanical ventilation discontinuation - End time (CPB) + 1) -
sum of all ventilation breaks with any ventilation break = Restart time - Stop time + 1

If a subject did not receive any mechanical ventilation the length is set to 0. For subjects who died before discharge from the hospital or before Day 28, respectively, the observed length of time on mechanical ventilation will be used. As sensitivity analyses subjects who died will (1) be excluded from analysis and (2) be assigned a length of time on mechanical ventilation of 28 days.

Length of time of inotrope use will be measured until the subject is discharged from the hospital or until Day 28, whichever occurs first. The length will be derived as the time in minutes from separation from CPB (variable "End time" of parameter "CPB" from section "Post incision" on CRF "Surgery") until last use (last "end date/time" of any medication as documented in section "Inotropes" on CRF "Inotropes and Vasoactive Medications").

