- Length of time of inotrope use (min) =
Last "end date/time" of any inotrope - End time (CPB) + 1

Any interruptions will discontinue to accrue, any duration of re-use will continue to accrue. If a subject did not use any inotropes the length is set to 0. For subjects who died before discharge from the hospital or before Day 28, respectively, the observed length on inotropes will be used.

As sensitivity analyses subjects who died will (1) be excluded from analysis and (2) be assigned a length of time on inotropes of 28 days. Hypothesis to be tested:

H0: Composite endpoint within the L-citrulline group is equal to that of the placebo group

H1: Composite endpoint within the L-citrulline group is unequal to that of the placebo group

H0 will be tested using a Wilcoxon-rank-sum test. The level of significance is 1% (two-sided).

As additional sensitivity analyses, the composite endpoint will be derived with (3) length of time of inotrope use starting on first "start date/time" of inotrope use and (4) length of time of inotrope use starting on first "start date/time" of inotrope use and length of time on mechanical ventilation starting on "start date/time" of mechanical ventilation. For sensitivity analyses (3) and (4) the observed length on mechanical ventilation/ inotropes will be used for subjects who died.

The FAS will be the primary analysis set for the analysis on the composite endpoint. Analyses using the mFAS and the PP serve as sensitivity analyses.

Two-sided 95% confidence intervals using Hodges-Lehman method will be additionally calculated.

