4.8 Missing Values

Efficacy endpoints describing length of time

If a subject did not receive any mechanical ventilation / inotropes / positive pressure ventilation / intubation / vasodilators / chest tube, the corresponding length of time is set to 0. For subjects who died before discharge from the hospital or before Day 28, respectively, the observed length of time will be used for analysis of all time variables.

For time to event analyses censoring information will be used for statistical analyses.

No other imputation of missing values will be used.

Efficacy endpoint inotrope score

The total inotrope score will be set to zero after the bypass pump has been removed. It will also be set to zero for patients not using inotropes at all.

Further secondary efficacy endpoints

No imputation of missing values will be applied for the secondary endpoints hemodynamic improvement, volume of chest tube drainage, and L-citrulline plasma levels.

Safety endpoints

For laboratory data, concentrations below the limit of quantification will be set to zero. Missing safety data or safety assessments will not be estimated nor imputed. All safety summaries and analyses will be based on observed data.

No other imputation of missing values will be used.

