Actually the exact start and end date/times of inotropes will be documented in the CRF, therefore the length of time of inotrope use will be derived in minutes.

Additionally, to be consistent to the time of mechanical ventilation, the time of separation from CPB will be used as starting point instead of time of first use.

Also, it is stated "For any missing scores between two non-missing scores they will be imputed using the most recent non-missing score (the last observation carried forward principle)." Due to the inotrope documentation as described above the LOCF principle is not to be applied.

6 Literature

n/a

7 Appendices

- Appendix A: List of generated summary tables, listings, and graphs

8 Signatures**Statistician:**

[name]
FGK Clinical Research GmbH
[name]
[name]
Germany

04 Oct 2018

Date (ddmmmyyyy)

[name]

Signature

Sponsor:

[name]
Aklepion Pharmaceuticals, LLC
Chief Medical Officer
[name]
[name]

02 Oct 2018

Date (ddmmmyyyy)

[name]

Signature

[name], BA
Aklepion Pharmaceuticals, LLC
Director of Clinical Operations
[name]
[name]

02 October, 2018

Date (ddmmmyyyy)

[name]

Signature

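### The SAP's inotrope-duration formula turns negative when the last inotrope stops on bypass, so in one secondary endpoint that child ranks better than a child who needed none

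*SAP*

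**What the plan says.** **Recording window.** Protocol section 6.2.1.2 (Inotropes) states: "Inotrope use will be assessed from the start of CPB until the subject is discharged from the hospital or at Day 28". Among the tasks carried out in the operating room, protocol section 5.1.2.1 lists "Inotrope and other concomitant medication documentation". Inotropes given on bypass are therefore within what the trial collects.

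**Clock.** Protocol section 7.1.4 measures inotrope use from first to last use, which cannot be negative. SAP section 5 changes this: "the time of separation from CPB will be used as starting point instead of time of first use". SAP section 4.4.1 carries the change out ("The length will be derived as the time in minutes from separation from CPB") and gives the formula "Last 'end date/time' of any inotrope - End time (CPB) + 1".

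**Zero rule.** SAP section 4.4.1: "If a subject did not use any inotropes the length is set to 0". SAP section 4.8 repeats this rule for the time variables and closes with "No other imputation of missing values will be used". There is no lower bound and no restriction to use after separation.

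**Where it is used.** The length is one of the two components of the primary composite (section 4.4.1). It is also a secondary endpoint of its own, with the same definitions and the same rank and survival analyses (section 4.4.2). Section 4.4.2 describes all secondary analyses as exploratory.

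**The concern.** The SAP moved the start of the clock to separation from CPB but left the end of the clock open to any recorded inotrope, including one that had already stopped by then. For a child treated only on bypass, the end precedes the start. The zero rule does not catch this child, because an inotrope was used.

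Post-operatively this child is identical to one who never had an inotrope, and the SAP's objective concerns post-operative need. Yet the formula places the child below zero, so treatment on bypass scores as better than no treatment. In the Kaplan-Meier, log-rank and Cox analyses of the same endpoint, a time before the origin has no meaning, and the SAP does not say what to do with it. The inotrope result matters to readers because it is one of the two parts by which the composite will be interpreted.

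**Working it through.** **The plan's own figure.** The planned 92 per group (SAP section 1.3) belongs to the composite and is not in dispute. It reproduces with Noether's formula: effect size 0.600 gives P = Φ(0.6/√2) = 0.6643, and n = (z0.995 + z0.90)² / [6(P - 0.5)²] = 91.85, rounded up to 92.

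**When the formula turns negative.** Let c be the CPB end time and e the last inotrope end time, in whole minutes. Length = e - c + 1, which is below 0 when c - e is 2 or more. With c set at minute 120 for illustration:

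| Last inotrope ended | Formula | Length (min) |
|---|---|---|
| Never used | zero rule | 0 |
| 90 min before CPB end | 30 - 120 + 1 | -89 |
| 30 min before | 90 - 120 + 1 | -29 |
| 2 min before | 118 - 120 + 1 | -1 |
| 1 min before | 119 - 120 + 1 | 0 |
| At CPB end | 120 - 120 + 1 | 1 |
| 60 min after | 180 - 120 + 1 | 61 |

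**Effect on ranks.** Take seven children: three never-users (0, 0, 0), one bypass-only child (-29), and three with lengths of 61, 481 and 1381 minutes. As written, the bypass-only child has rank 1 and each never-user rank 3. With the length set to 0, all four share rank (1 + 2 + 3 + 4)/4 = 2.5. The other three keep ranks 5, 6 and 7 in both cases.

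**Effect on the composite.** The composite is max(ventilation, inotrope length), and ventilation is 0 if there was none. For the child at -29: unventilated, max(0, -29) = 0; ventilated until 360 minutes after separation, 360 + 1 = 361 and max(361, -29) = 361. Replacing -29 by 0 changes neither value.

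**Effect on the survival sets.** SAP section 4.4.1 defines three sets. Carried over to inotrope use alone, they treat a non-user as follows:
- Set (1) keeps the non-user at 0 as an uncensored observation. The bypass-only child should be there too but has an invalid time. Losing the child here changes the analysis.
- Set (2) censors the non-user at 0, where the child adds essentially nothing to later risk sets. Losing the bypass-only child gives almost the same result as handling the child correctly.
- Set (3) deletes the non-user. Losing the bypass-only child gives the same result as handling the child like a never-user.

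**Effect on the error rate.** The rule is the same in both arms. Simulation used 92 per arm, 2,000 data sets per setting, 20% never-users and skewed positive durations. With the same assumed bypass-only share of 5%, 10% or 20% in each arm, the 5% Wilcoxon test rejected in 4.7%, 4.3% and 6.1% of data sets with negative values kept, and in 4.9%, 4.3% and 5.7% with them set to 0. The shares and distributions are assumptions, not figures from the documents.

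**The case against.** The strongest reply is that the intended value is obvious. Time from separation to a last use that came earlier is an empty interval, the objective is post-operative, and the hourly inotrope score in SAP section 4.4.2 also begins at separation. A sensible programmer would enter 0. The endpoint is one of eleven secondary efficacy variables, has no formal hypothesis and is labelled exploratory. The CRF page is not shown, so no document proves that any child will have inotropes on bypass only. Section 4.4.2 also includes a sensitivity analysis timed from first use, which cannot go negative.

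Most of this stands and keeps the point small, but it does not remove it. The written formula gives a definite wrong value, and a pre-specified derivation should not rest on a programmer's guess. The same SAP section restricts vasodilator time to use after separation, so the missing restriction for inotropes is an inconsistency. The first-use sensitivity analysis answers a different question, because it counts minutes on bypass; it does not repair the main analysis.

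A reader might infer that sensitivity analyses (3) and (4) also need changing. They do not: they keep the protocol's first-use start and give no negative lengths. Restricting them to use after separation would remove the check that they provide on the SAP's change of origin.

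**Conclusion.** Wrong as written; minor. The formula gives a negative length to any child whose last recorded inotrope stopped 2 minutes or more before separation. In the Wilcoxon analysis of the secondary endpoint that child ranks better than a never-user. In its survival analyses the value is invalid, with a real difference mainly in set (1).

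Three stronger readings are tempting and are not supported:
- That the primary result is at risk. The composite takes the longer length and ventilation is never below 0, so its values and its Wilcoxon test do not change.
- That many children are affected or lost. The documents give no share, so the number cannot be determined.
- That the false-positive rate is inflated. With no treatment difference, an identical rule in both arms keeps the test at its level. The harm is a wrong ordering, and p-values can shift if bypass-only use is common or differs by arm.

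The conclusion assumes that inotropes given on bypass reach the CRF section that the formula reads, as protocol sections 6.2.1.2 and 5.1.2.1 imply, and that the formula is programmed literally.

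**What to change.** In SAP sections 4.4.1 and 4.4.2, state that for the length timed from separation from CPB only inotrope use after separation counts, and that the length is 0 if there is none. Add that such children are treated as having no inotrope use in survival sets (1) to (3). The vasodilator paragraph of section 4.4.2 already restricts use in this way and can serve as a model. Leave sensitivity analyses (3) and (4) unchanged.

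The cost is a sentence or two in the SAP and a line or so of code, settled before unblinding. No new data are needed, and the sample size and the primary test stay as they are. If no such child exists, nothing changes.

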Two-sided 95% confidence intervals using Hodges-Lehman method will be additionally calculated. Survival analyses using Kaplan-Meyer estimates and plots, log-rank test and Coxregression modeling will serve as sensitivity analyses.

For survival analyses, different sets of analyses will be done:

- (1) The composite variable for subjects without any mechanical ventilation and without any use of inotropes is set to 0, observations will not be censored
- (2) The composite variable for subjects without any mechanical ventilation and without any use of inotropes is set to 0, observations will be censored
- (3) Subjects without any mechanical ventilation and without any use of inotropes will be deleted from analysis

Subjects who receive mechanical ventilation or are still using inotropes on the last day of observation (which can be Day 28, day of early discontinuation, or day of death) will be censored for survival analyses.

Analysis of Secondary Efficacy Endpoints

No formal statistical hypotheses are specified for the secondary endpoint variables. Nonetheless statistical testing methods will be applied to compare treatment groups. A significance level of 5% (two-sided) will be used for such analyses. Secondary efficacy endpoints will be analyzed using the FAS, mFAS and the PP.

Length of Time on Mechanical Ventilation

The same definitions and analyses as described for the primary endpoint will be applied.

Length of Time on Positive Pressure Ventilation

The same definitions and analyses as described for the primary endpoint will be applied.

Length of Time of Inotrope Use

The same definitions and analyses as described for the primary endpoint will be applied.

Inotrope Score

The total inotrope score at each hour post-operatively from the time of separation from bypass, until the completion of study drug will be calculated as:

Total Inotrope Score = Dopamine + Dobutamine + 10*Milrinone + 100*Epinephrine + 100*Phenylephrine + 100*Norepinephrine.

The total inotrope score will be summarized at each post-operative hour and analyzed using a Wilcoxon-Rank sum test and an analysis of variance (ANOVA) with a fixed effect for treatment group. Also, a repeated measures analysis of variance will be used to compare total inotrope score between placebo and L-citrulline over time.

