1.3 Sample Size Calculation

Sample size was calculated with nQuery 7.0. Assuming a standard deviation of 50 and mean values of 44 for placebo and 14 for the L-citrulline group, the effect size is estimated being 0.600, which yields a sample size of N=92 per group when applying a two-sided Wilcoxon-rank-sum test with a 0.01 significance level and a power of 90%. The assumptions concerning standard deviation and mean values are based on results of the preceding study CIT-002-01.

To allow for subjects being enrolled but not assigned to the full analysis set (FAS), an overall N=95 subjects per group will be enrolled. A sample size re-estimation will be done within the framework of an interim analysis (see section 1.4).

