Survival analyses using Kaplan-Meier estimates and plots, log-rank test (significance level of 5%) and Cox-regression modeling including factor treatment (no further factors to be included) will serve as sensitivity analyses. For subjects who died before discharge from the hospital or before Day 28, respectively, the observed length of time on mechanical ventilation/inotropes will be used. The sensitivity analyses (1) and (2) as described for the primary analysis (subjects who died will (1) be excluded from analysis and (2) be assigned a length of time on inotropes of 28 days) will not be applied for survival analyses. The sensitivity analyses (3) and (4) as described for the primary analysis (composite endpoint will be derived with (3) length of time of inotrope use starting on first "start date/time" of inotrope use and (4) length of time of inotrope starting on first "start date/time" of inotrope use and length of time on mechanical ventilation starting on "start date/time" of mechanical ventilation) will be applied for survival analyses. For survival analyses different sets of analyses will be done:

(1) The composite variable for subjects without any mechanical ventilation and without any use of inotropes is set to 0, observations will not be censored

(2) The composite variable for subjects without any mechanical ventilation and without any use of inotropes is set to 0, observations will be censored

(3) Subjects without any mechanical ventilation and without any use of inotropes will be deleted from analysis

For sensitivity analyses (3) and (4) the first set of analyses (i.e., (1) The composite variable for subjects without any mechanical ventilation and without any use of inotropes is set to 0, observations will not be censored) will be used.

Subjects who receive mechanical ventilation or are still using inotropes on the last day of observation (which can be Day 28, Day of early discontinuation, or Day of death) will be censored for survival analyses.

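### The primary composite is tested at two-sided 1%, but its only planned effect interval is 95% and the SAP reads its log-rank check at 5%, with no rule for a p-value between the two.

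*SAP*

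**What the plan says.** **Primary test.** SAP 4.4.1 states: "H0 will be tested using a Wilcoxon-rank-sum test. The level of significance is 1% (two-sided"). Protocol 7.1.4 and the synopsis set the same level. The sample size uses it too (SAP 1.3, protocol 7.2). An effect size of 0.600 is assumed there, and SAP 1.3 continues: "which yields a sample size of N=92 per group when applying a two-sided Wilcoxon-rank-sum test with a 0.01 significance level and a power of 90" per cent.

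**Effect interval.** SAP 4.4.1 adds: "Two-sided 95% confidence intervals using Hodges-Lehman method will be additionally calculated". Protocol 7.1.4 and the synopsis also give 95%. No 99% interval is planned in either document.

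**Survival analyses of the same composite.** SAP 4.4.1 plans "Survival analyses using Kaplan-Meier estimates and plots, log-rank test (significance level of 5%) and Cox-regression modeling" as sensitivity analyses. It attaches the 5% level to the log-rank test only. Protocol 7.1.4 gives no level: "log-rank test and Coxregression modeling will serve as sensitivity analyses". SAP section 5, which lists changes from the protocol, does not mention the added 5%.

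Neither document explains why the levels differ. Neither says how to read an interval that excludes zero, or a log-rank p-value below 0.05, when the primary p-value is 0.01 or more.

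**The concern.** A Hodges-Lehmann interval is obtained by inverting the Wilcoxon test. The interval that agrees with a 1% test is therefore the 99% interval, and a 95% interval agrees with a 5% test. As planned, the estimate that readers will quote for the primary endpoint follows a looser standard than the decision it accompanies. So does the named supportive test.

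At stake is how a failed primary test would be described. With a Wilcoxon p-value of 0.02, say, the report would show no significance at 1%, an interval clear of zero, and possibly a log-rank test marked significant. The situation is foreseeable in this programme. Protocol 1.4 already reads Phase IB log-rank p-values of 0.0498 (beside 0.0089 from another handling of zeros) and 0.0351 as evidence of shorter ventilation and inotrope use. The inotrope figure becomes 0.562 when patients with no inotrope use are censored. The present SAP plans at least five log-rank analyses of the composite in the full analysis set: three ways of handling zeros, plus sensitivity analyses (3) and (4).

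**Working it through.** **Inputs.** Means 44 and 14, SD 50, effect size 0.600, 92 per group, alpha 0.01 two-sided, power 90% (SAP 1.3; protocol 7.2). Interval level 95% and log-rank level 5% (SAP 4.4.1). I take the means to be in hours, the protocol's unit for the endpoint, and the 5% to be two-sided.

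**Step 1: reproduce the plan's N.** Noether's formula is n per group = (z(0.995) + z(0.90))² / (6 (P − 0.5)²).
- P = Φ(0.6/√2) = 0.6643.
- n = (2.576 + 1.282)² / (6 × 0.1643²) = 91.85, so 92. This matches the plan.
- At 5% the same formula gives 65, so the sizing does use 1%.

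**Step 2: when interval and test disagree.** Apart from ties, the 95% interval excludes zero when p < 0.05. The primary test succeeds when p < 0.01. They disagree when 0.01 ≤ p < 0.05.

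**Step 3: probability of that range, 92 per group.**
- No effect: 0.05 − 0.01 = 4% (simulated 3.8-4.0%).
- Planned effect 0.6: power = Φ(√(6 × 92) × 0.1643 − z). This is 90.1% at 1% and 97.1% at 5%, a difference of 7.1 points. Simulations with normal data gave 6.2% to 7.1%.
- Effects of 0.3 and 0.4 (assumed; neither is in the documents): about 22-24%.

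**Step 4: sensitivity to shape.** Step 3 assumes a normal shift with equal spread. The endpoint is a duration bounded at zero, and the Phase IB SDs were 63.62 and 14.06 (protocol 7.2, Table 2). Under assumed skewed shapes at 92 per group, the same probability was:
- lognormal with the Table 2 means and SDs: about 0%;
- gamma with the Table 2 means and SDs: about 21%;
- gamma with means 44 and 14, SDs 50 and 14: 0.3%.

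**Step 5: the log-rank test.** Simulated without censoring (exponential or lognormal data under no effect, normal shift otherwise):

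| Scenario | Interval excludes 0, primary fails | Log-rank p < 0.05, primary fails | Both |
|---|---|---|---|
| No effect | 3.8-4.0% | 4.2-4.7% | 1.8-2.1% |
| Effect 0.6 | 6.2% | 5.2% | 4.7% |
| Effect 0.3 (assumed) | 24% | 21% | 15% |

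**Step 6: the gap in hours.** The critical value is P = 0.5 + z/√(6 × 92), converted to a shift by 50 × √2 × Φ⁻¹(P). The 1% test needs an observed shift of about 19.7 h (0.39 SD). The 95% interval clears zero from about 14.9 h (0.30 SD).

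**Step 7: width and an example.** The ratio of 99% to 95% width is about 2.576/1.960 = 1.31. In one simulated trial with Wilcoxon p = 0.021, the 95% interval was 2.8 to 31.6 h and the 99% interval −1.8 to 36.4 h. Only the 99% interval agrees with the failed 1% test.

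**The case against.** The decision rule is clear: one test, one level, one primary analysis set. The plan ranks the interval as additional and the survival analyses as sensitivity analyses, so neither can rescue a failed primary test. A 95% interval is a common default for estimation. The same analyses also carry over to the secondary duration endpoints, which are tested at 5% and called exploratory, so a single interval level is convenient. A reader who sees p = 0.02 beside the 1% threshold need not be misled.

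Most of this stands, and it limits the point to reporting and interpretation. It does not remove it. The exploratory label in SAP 4.4.2 covers the secondary analyses, not the interval or the log-rank test of the primary endpoint. Convenience for secondary endpoints also does not explain why the primary endpoint has no interval at its own level.

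Three further limits stand:
- The match between test and interval is approximate when many subjects share the value zero.
- The log-rank test weights the data differently and uses censoring. A 1% level would reduce its disagreement with the Wilcoxon test but not remove it.
- The probabilities depend strongly on the shape of the data.

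A reader might infer that the looser levels inflate the type I error, or that a failed primary test would regularly come with both an excluding interval and a significant log-rank test. The documents support neither. Success depends only on the 1% Wilcoxon test. The interval conflict follows almost automatically in the p-value range, but the log-rank conflict is only possible: under no effect, both occur together in about 2% of trials.

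**Conclusion.** The mismatch is real and modest. For the primary composite, the planned interval and the SAP's log-rank level are looser than the 1% decision rule, and no rule covers a Wilcoxon p-value from 0.01 up to 0.05. The 95% interval is in both documents; the 5% log-rank level is in the SAP alone.

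The 4% under no effect follows from the nominal levels. The 6-7% at effect 0.6 rests on the plan's own inputs and a normal shift. The 22-24% rests on assumed effects of 0.3-0.4; these are plausible because the planned effect comes from 11 patients per arm, but they remain assumptions. The skewed alternatives ranged from about 0% to 21%, so none of the figures with a treatment effect should be read as a forecast. The point is worth acting on because the remedy costs so little.

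**What to change.** **Interval.** In the protocol synopsis, protocol 7.1.4 and SAP 4.4.1, name a 99% Hodges-Lehmann interval as the one that matches the primary test. Keep the 95% interval as a labelled supplement. All three places need the change; otherwise a new inconsistency arises.

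**Survival analyses.** In SAP 4.4.1, do one of two things:
- replace the 5% log-rank level with 1%; or
- state that the log-rank and Cox results for the primary endpoint are descriptive and cannot support an efficacy claim if the 1% Wilcoxon test fails.

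The second is simpler and also covers disagreement that a common level would leave.

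**Cost.** A few lines of wording and one more table column, fixed before unblinding. The matching interval is about 31% wider than the 95% interval. N stays at 92 per group, because the sizing already uses 0.01.
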